- 4) Determine inter-observer variability/concordance for pathology and echo-Doppler examination.
- 5) Describe the cost-result of the algorithm

4. Research design

4.1-Precise statement of the main evaluation criteria and, where applicable, the secondary evaluation criteria

4.1.1-Main evaluation criterion

The number of patients with an alternative diagnosis in the 2 years of follow-up among patients considered to have GCA on clinical and biological suspicion + "positive" echo-Doppler.

4.1.2-Secondary evaluation criterion(ies)

- 1) To assess the criteria to be taken into account to establish a diagnostic score, the number of patients per collected variable will be determined according to the diagnosis of GCA confirmed or not.
- 2) The number of positive TAB will make it possible to calculate the rate of "positive TAB" in the "negative" CDU group. The frequency of vasculitis lesions of the vasa vasorum (VVV) and/or periadventitial vessels (VPA) will be established in this "negative" CDU group. Patients in the GCA group diagnosed by CDU will be compared to the group of GCA patients diagnosed by TAB for clinical and biological data.
- 3) The description of the evolution of the halos at W3/W4 will make it possible to study whether there is any correlation with the rate of corticosteroid-dependent patients, the number of relapses, ischemic complications, etc...
- 4) The number of TAB slide reading discrepancies will be established, and its corollary, the number of inter-operator discrepancies on the echo-Doppler.
- 5) Diagnostic costs (consultation and/or hospitalization, CDU and TAB), induced costs (complication, adverse event of TAB), avoided costs (absence of TAB for CDU positive patients), and indicators of efficacy (positive diagnosis rate according to the CDU, according to the diagnostic algorithm (CDU +/- TAB), number of Horton's disease successfully treated at 2 years of follow-up and the number of patients for whom the surgery could be avoided) will be determined.

4.2-Description of the research methodology

4.2.1-Experimental plan

Diagnostic study in internal medicine, cross-sectional, prospective, regional multicenter.

4.2.2-Procedure of the study

4.2.2.1-Inclusion

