In each of the centres, patients over 50 with a clinical suspicion of GCA, established by the expert clinician, receive oral and written information concerning the protocol, its objectives and its constraints. A period of reflection is granted to the patients before collecting their non-objection to participate in the study.

The inclusion of the patient in the study will be mentioned in the patient file, it will specify the methods of collecting the non-objection as well as that of the information.

Patients agreeing to participate will be looked after by supervisors who will respect the diagnostic algorithm described below.

The minimum biological assessment will consist of a blood count and a CRP assay. The sedimentation rate (ESR), the assay of Gamma glutamyl transpeptidase (GGT) and alkaline phosphatase (ALP) will be optional measurements.

The investigator assigns an identifier (number and initials) to the patient in order to guarantee the anonymization of the data.

This identifier will be in the following form:

Center number and patient number: I____I____I____I - I____I____I____I

Patient initials (Last name - First name): I____I - I____I

The patient number is given incrementally (ie in the order of the consent signatures).

The local investigator keeps a table of correspondence between the identity and the patient code, which will be destroyed at the end of the study.

4.2.2.2-Subject follow-up

DIAGNOSTIC ALGORITHM

Visit 1: Doppler echo examination

In case of clinical suspicion of GCA, an CDU will be carried out within 7 days following the initiation of corticosteroids.

Visit 2: consultation with the internist within 7 days after the Doppler ultrasound

The diagnostic orientation criteria will be as follows:

- The observation of a clear hypoechoic halo on two non-contiguous arterial segments will confirm the diagnosis of GCA, the patient will not undergo TAB.
- In the event of a negative CDU examination, the patient will undergo a TAB

Visit 3:consultation with the internist (maximum 3-4 weeks after initiation of corticosteroid therapy)

For patients with positive CDU n°1, a requested CDU n°2 (via a voucher informing the patient's participation), will be carried out between 3 and 4 weeks after the start of corticosteroid therapy:

- If a Halo is observed on the axillaries and/or primitive carotids, a PET-CT or injected CT will be performed to look for aortitis.

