- If the Halo persists at W3/W4 (the clinical significance is unknown), a visit to M3 with the same operator (CDU n°3) will be offered to the patient.

For patients with negative CDU n°1, the results of the TAB will be collected:

- If this is positive, patients will be followed in the same way as patients with a positive CDU.
- If the TAB is negative:
 - o Either Horton's diagnosis will be retained and the patient will have the same follow-up as those with a positive CDU or a positive TAB
 - o Either an alternative diagnosis will be considered, and the diagnostic and therapeutic care of the patient will be left to the discretion of the doctor, and noted in a specific follow-up.

FOLLOW UP

Visits 4 (M3), 5 (M6), 6 (M12), and 7 (M24): follow-up consultation by the internist

Data on disease progression and treatment will be collected.

For patients with an alternative diagnosis, follow-up at M3, M12 and M24 can be done by telephone.

[figure not shown]

figure1: diagram of the diagnostic algorithm (GCA: giant cell temporal arteritis; TAB: temporal artery biopsy; CT: corticosteroid)

	V0 D0 inclusio n	V1 < 7 d CT	V2 < 7 d of CDU	V3 3-4 weeks after CT	V4 M3	V5 M6	V6 M12	V7 M24
Information	X							
Consent	X							
Eligibility criteria	X							
Demography	X							
Clinical signs	X			X	X	X	X	X
Biology report	X					X	X	
Treatment	X		X	X	X	X	X	X
Support mode	X	X	X	X				
Arterial Doppler echo		X		X*	X*			
CDU or TAB appointment			X					
TAB result				X*				

Tableau 1: data collection schedule (* see diagnostic algorithm)

4.3-Description of the evaluation parameters and the methods to measure, collect and analyze these parameters

4.3.1-GCA diagnostic criteria according to the American College of Rheumatology 1990

- 1) Age greater than or equal to 50 years at onset of symptoms
- 2) Unusual headaches
- 3) Clinical abnormalities of the temporal arteries such as pain on palpation or decreased temporal pulse or claudication of the jaw
- 4) Increase in ESR > 50 mm at the 1st hour
- 5) Infiltrates of granulocytes or mononuclear cells with usually the presence of giant cells in the arterial wall

Probable diagnosis if 3 or more criteria

Sensitivity of 94% and specificity of 91%

4.3.2- Color Doppler Ultrasound Protocol

- Longitudinal and transverse examination of the bilateral subclavian, axillary, vertebral, superficial femoral and superficial temporal arteries.
- Blinding of the degree of clinical suspicion of the practitioner

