The analysis of the primary endpoint will consist of determining the positive predictive value of CDU and the algorithm will be considered valid in the absence of an alternative diagnosis within 2 years of follow-up in the group considered to have GCA. on a clinical-biological suspicion + "positive" echo-Doppler.

To establish a probability model of the clinical and paraclinical score calculation type, the variables significantly associated with the diagnosis will be determined by logistic regression. A number of points will be assigned to each variable based on the strength of its association with the diagnosis. The area under the ROC curve will be used as an indicator of the discriminative power of the score.

Correlation analyzes will be carried out to study a possible link between the description of the halos and the persistence of a poorer clinical response and to evaluate the inter-operator reproducibility for the reading of the TAB slides and Doppler echo images.

The analysis of diagnostic costs, induced costs, avoided costs, and efficiency indicators will make it possible to determine the costs/results of the diagnostic algorithm.

7.2- Expected number of people to be included in the research, and expected number of people in each research location with its statistical justification

According to a retrospective study of 42 patients treated for suspected Horton's disease, 70% of them had their Horton's diagnosis confirmed. To include at least 100 patients with Horton's disease over the study period, it is therefore necessary to include at least 142 patients suspected of Horton's disease (100 confirmed Horton's/42 other diagnoses). To take into account the possible overestimation of confirmed cases of Horton's disease due to biases of the retrospective study, the objective is to include 168 patients suspected of Horton's disease.

The population over 50 represents just over one million inhabitants in Charente-Maritime, Deux-Sèvres and Vienne. Considering an incidence of 1.2/10,000 inhabitants, approximately 120 new cases of Horton are detected each year.

Department	Number of people over 50	Number of new cases of Horton per year	Number of new Horton cases over 24 months	Estimation of the number of suspected cases of Horton over 24 months
Charente Maritime	491 871	59	118	168
Vienna	284,078	34	68	97
Two Sevres	261 272	31	63	90
Total	1037221	124	249	355

Table 2: theoretical recruitment potential

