Knowing that the diagnosis of GCA is difficult, the majority of patients likely to be carriers of Horton are referred to clinicians. However, to account for patients not cared for by monitors participating in the study and patients refusing to participate, the goal is to include 45-50% of suspected Horton cases.

Center	Recruitment objective (Nb patients/month)	Duration of inclusion (months)	Forecast over the entire duration of the study
La Rochelle	2	24	48
Rochefort	1.5	24	36
Poitiers	2	24	48
Niort	1.5	24	36
Angouleme	1	24	24
Nantes	2	12	24

Table 3: goal of inclusion

7.3- Expected degree of statistical significance

The statistical tests will be carried out at the bilateral alpha risk of 5%.

7.4- Statistical criteria for stopping research

An interim analysis at 1 year of the start of inclusions will be made. Depending on the results (absence or presence of an alternative diagnosis in the group considered to have GCA on a clinical-biological suspicion + "positive" echo-Doppler) the study will be continued or not.

7.5- Method for taking into account missing, unused or invalid data

In case of premature termination and non-compliance with the protocol, the reasons will be documented. Missing data will be described in terms of numbers and corresponding percentages for each criterion and at each visit. There are no plans to replace patients exiting the study.

Patients suspected of Horton's disease are treated with corticosteroids. The administration of this treatment requires regular dose reviews. Patients are therefore monitored regularly in current practice and few loss of follow-up are expected in the study. On the other hand, cortisone treatment allows a good clinical evolution in patients with gigantocellular arteritis and the response to treatment in the very old subject seems comparable to that of the younger subject. The expected death rate is therefore that of the general population of the same age. Thus, if less than 5% of the patients in the study are lost to follow-up or died, the missing data will be replaced by deductive imputation when possible (e.g. patients with a combination of clinical signs, biological and examinations in favor of a horton and a good evolution under corticosteroids will be classified as suffering from Horton's disease). In the event of a higher rate of missing data, other methods of managing problematic data will be considered.

7.6- Management of modifications made to the analysis plan of the initial strategy

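### The PPV of CDU is judged against a diagnosis that CDU itself sets and that nobody blinded to CDU re-examines, so missed false positives favour the zero-event success rule

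*Combined protocol and SAP*

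**What the plan says.** Section 4.2.2.2 gives the rule at Visit 2: "The observation of a clear hypoechoic halo on two non-contiguous arterial segments will confirm the diagnosis of GCA, the patient will not undergo TAB". The patients to whom it applies already carry a suspicion of GCA and a raised CRP (5.1).

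The primary criterion in 4.1.1 is "The number of patients with an alternative diagnosis in the 2 years of follow-up among patients considered to have GCA", that group being defined by clinical-biological suspicion plus a positive CDU. Section 7.1 turns this into a PPV and a success rule: "the algorithm will be considered valid in the absence of an alternative diagnosis within 2 years of follow-up". The one-year interim decision in 7.4 rests on the same event.

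The internist acts on the CDU result early ("Visit 2: consultation with the internist within 7 days after the Doppler ultrasound") and follow-up is again by the internist: "Visits 4 (M3), 5 (M6), 6 (M12), and 7 (M24): follow-up consultation by the internist". Of the content of those visits 4.2.2.2 says "Data on disease progression and treatment will be collected". Table 1 has no row for a final or revised diagnosis. The only written branch in which an alternative diagnosis is considered concerns CDU-negative, TAB-negative patients.

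Blinding is stated in three places: the CDU operator with respect to the degree of clinical suspicion, the expert re-read of the images (both 4.3.2), and the expert re-read of the biopsy slides (4.3.4). None covers the final diagnosis.

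If fewer than 5% of patients are lost or die, section 7.5 allows deductive imputation. Its example assigns GCA to "patients with a combination of clinical signs, biological and examinations in favor of a horton and a good evolution under corticosteroids".

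**The concern.** A CDU-positive patient counts as a true positive by default. The patient becomes a false positive only if a clinician, not blinded to the CDU, replaces the label. The plan does not say what evidence makes an alternative diagnosis in this group, nor that the evidence must be separate from CDU. Under 7.5 the CDU can also count among the favourable examinations that turn a missing outcome into GCA.

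If clinicians are at all slow to overturn a positive CDU, the estimate counts unrevised labels rather than verified disease. Because success means zero events, each unrevised false positive bears directly on the verdict, and also on the interim decision.

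The plan itself treats false positives as possible. Section 2.1 calls the specificity problem negligible only under listed conditions, and the reference list in 2.4 includes reports of a halo in another temporal artery disorder and of amyloidosis simulating GCA. Amyloid is among the lesions sought on biopsy (4.3.4), which CDU-positive patients do not have.

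**Working it through.** **The plan's own figure.** Section 7.2 wants 100 GCA patients at 70% confirmed: 100 / 0.70 = 142.9, against a stated 142, which agrees to rounding. The target of 168 has no formula; it implies 100 / 168 = 59.5% confirmed. Neither figure concerns the PPV. The plan states no target PPV, precision or power for the primary analysis, so there is nothing further to reproduce.

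**Number of CDU-positive patients, n.** The plan does not give it. Three values follow from its figures (sensitivities of 69% and 96% in 2.1):
- 100 × 0.69 = 69
- 100 × 0.96 = 96
- 168 × 0.70 × 0.96 = 112.9, or 113

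These are expected true positives. Adding false positives raises n slightly: at a PPV of 95%, 69 / 0.95 = 72.6. With n = 73 the first and last entries of the n = 69 column below become 2.4% and 40%, so the picture does not change.

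**Effect of under-revision.** Let d be the share of false positives later recorded as an alternative diagnosis. The documents give no value for d or for the true PPV; both are assumptions.
- Recorded PPV = 1 − (1 − true PPV) × d
- Chance of zero events = (recorded PPV)^n

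With true PPV = 95%:

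| d | Recorded PPV | n = 69 | n = 96 | n = 113 |
|---|---|---|---|---|
| 1 (all revised) | 95.0% | 2.9% | 0.7% | 0.3% |
| 0.5 | 97.5% | 17.4% | 8.8% | 5.7% |
| 0.25 | 98.75% | 42.0% | 29.9% | 24.1% |

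Range over the true PPV at n = 69, from d = 1 to d = 0.25: at 90%, from 0.07% to 17.4%; at 97%, from 12.2% to 59.5%; at 99%, from 50.0% to 84.1%. At 100% there are no false positives, and d has no effect.

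**Effect of imputation.** The 5% threshold applies to all patients in the study. Assuming losses fall evenly, just under 5% means 3 of 69 (5% is 3.45) or 4 of 96 (5% is 4.8). If all are imputed as GCA and no event is seen, the reported PPV is 100%. Counting them as not confirmed gives 66 / 69 = 95.7% or 92 / 96 = 95.8%.

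**Precision without any bias.** With zero events the exact two-sided 95% lower limit is 0.025^(1/n): 94.8% at n = 69 and 96.2% at n = 96.

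**The case against.** The strongest defence is that two years of follow-up is a legitimate delayed clinical reference: CDU sets the initial label, and the endpoint is what happens afterwards. Omitting TAB after a positive CDU is the strategy under study, not an analysis choice. Both points stand. They do not make the reference independent of CDU. The second CDU at 3 to 4 weeks is the same test, and the aortic imaging at Visit 3 is triggered by a halo.

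The revision shares and PPVs above have no source in the plan, and the only numerical specificity in 2.1 is 100%, from 20 patients. That also stands, and it is why the table is an illustration, with a no-bias case.

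The imputation point is limited. Section 7.5 does not name CDU, asks for several kinds of evidence together, and applies only below 5% losses. But CDU is an examination, nothing excludes it, and under a zero-event rule a few patients matter.

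A reader might infer two stronger things. One is that CDU alone makes the diagnosis. The plan requires clinical-biological suspicion and a raised CRP as well, so CDU decides only within a selected group. The other is that one and the same internist makes and later reviews the diagnosis. The text says the internist at each visit and never states that it is one person. The absence of blinding is likewise read from Visit 2 and from the three places where blinding is stated; the plan does not declare it.

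**Conclusion.** The point holds as a limitation of the primary analysis that should be corrected in the analysis text. The reference is not independent of the index test, and 7.5 can bring the index test back in. Any under-revision of false positives moves the PPV and the success rule in the favourable direction.

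The size is unknown. With an assumed true PPV of 95%, revising only a quarter of false positives moves the chance of passing from between 0.3% and 2.9% to between 24% and 42%, depending on n. Imputing just under 5% of CDU-positive patients can show 100% where the worst case is about 96%.

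A reader might conclude that the reported PPV will be inflated by a known amount, or that the design invalidates it. The documents do not support that: they give neither the revision share nor the true PPV, and if there are no false positives there is no bias.

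**What to change.** 1. In 7.5, exclude every CDU finding from the evidence used to impute GCA in CDU-positive patients. Add a worst-case PPV in which lost or unverifiable CDU-positive patients count as not confirmed.
2. Keep the clinician-based PPV as primary. Beside it, report a sensitivity PPV against a rule fixed in advance that uses no CDU field and only data already collected: for example the ACR 1990 items in 4.3.1, clinical signs and biology at the scheduled visits, other imaging where done, and recorded other diagnoses. Classify each CDU-positive patient as supported, not supported or alternative, and report how many cannot be classified.
3. State in 7.1 and in the conclusion that the PPV is measured against a clinical diagnosis not blinded to CDU.

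The text should say that item 2 is only a partial remedy. The data are recorded by staff who know the CDU, and recorded diagnoses are those clinicians' own. CDU-positive patients have no TAB, so the ACR histology item is unavailable. ESR is optional, Table 1 schedules biology at inclusion, M6 and M12 but not at M24, and the Visit 3 aortic imaging depends on a halo.

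The cost is analysis-plan text, the work of agreeing the rule, and programming; no added visit, procedure or assessor is needed. The downside is that some patients will be unclassifiable and the sensitivity PPV may look less favourable.

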PROCEDURE	
Since the reliability of Doppler ultrasound is technical and operator-dependent, a preliminary meeting for the study will make it possible to verify the technical prerequisites, to train the participating operators and to define a consensus for the interpretation of the halos.
 
In each of the centres, patients over 50 years of age with a clinical suspicion of GCA, established according to the levels of evidence described by the ACR recommendations, will be informed of the study by the supervising clinicians. Patients agreeing to participate will be cared for by clinicians who will respect the following diagnostic algorithm:
 
In case of clinical suspicion of GCA, an CDU will be carried out within 7 days following the initiation of corticosteroids. The minimum biological assessment will consist of a blood count and a CRP assay. The diagnostic orientation criteria will be as follows:
 
 - l'observation of a hypo haloChogene net on two non-contiguous arterial segments will confirm the diagnosis of GCA, the patient will not undergo TAB. - In the event of a single halo, the patient will undergo a TAB (of cohoyue of the halo), of meme in the absence of a halo sign. If the TAB is positive, patients will be followed in the same way as patients with a positive CDU. If the TAB is negative, the diagnostic

	
and therapeutic management of the patient will be left to the discretion of the doctor and noted in the follow-up.
 
Clinical follow-up of patients will include at least one internist/rheumatologist and angiologist visit between 3 and 4 weeks after the start of corticosteroid therapy (for treated patients) and a 2nd CDU between 3 and 4 weeks after the start of corticosteroid therapy for patients whose 1st CDU was positive:
 
 - If a Halo is observed on the axillaries and/or primitive carotids, a PET-CT-CT18FDG or an angio-CT of the aortic arch will be realized to check for aortitis. - If the Halo persists to S3/S4 (clinical significance is unknown), a visit to M3 with the same operator will be offered to the patient. 
Finally, internist/rheumatologist visits will be made at M3, M6, M12, M18, M24.
 
To ensure the standardization and reproducibility of interpretation of the CDUs, 4 meetings bringing together the operators will be organized at 2 months, 6 months, 12 months and 18 months.

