- diagnostic profitability: its sensitivity is imperfect with globally 20 to 30% of negative results. This result is partly due to the segmental and focal vascular tropism of the disease and to the existence of a more "proximal" form exclusively involving the aorta and its large trunks, but also to the difficulty of pathological diagnosis with an inter-observer variability not negligible (specimen size, number of cuts, doctor's experience, consideration of VVV and VPA (11-13). Thus, the result of the biopsy does not often influence the action to be taken by the practitioner (14) .

As a result, research over the past 20 years has aimed to develop alternative diagnostic means to TAB. This has notably been the case with color Doppler ultrasound since the description by Wolfgang A. Schmidt and collaborators of the halo sign on the superficial temporal arteries in 1995 (15).

Color Doppler ultrasound of ATS, subject to certain technical conditions (detailed later) and an experienced operator, is a non-invasive tool, at least as sensitive and very specific for the diagnosis of GCA as have shown well by recent studies and meta-analyses (16-18). A very recent study even showed a higher sensitivity of CDU compared to TAB for the diagnosis of GCA, 96% versus 67% for an identical specificity (119). CDU can additionally analyze other arterial segments potentially affected by disease. Thus the diagnostic performance of the CDU is further increased if the analysis concerns in addition to the ATS, the subclavian, axillary and common carotid arteries. (20).

Within the framework of a retrospective and monocentric study on the CH of La Rochelle (LR) we found results similar to those published with a sensitivity of 69% and a specificity of 100% of the CDU among 20 patients all suspected of 'GCA' (13).

From critical reading of the scientific literature and our experience, we believe that the specificity problem of CDU becomes negligible if the pre-test probability is high, if systemic necrotic vasculitis has been ruled out, if the operator is experienced and if the CDU positivity criteria are strictly defined (example: certain and bilateral character of the Halo, hypoechoic character of the halo, not taking into account the effects of stenosis on the ATS).

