- Duration of examination: 30 minutes, carried out as soon as possible after the request of the corresponding doctor (in practice within the following 48 hours according to our experience.)
- Ultrasound of the superficial temporal arteries (common trunk, frontal branch, parietal branch).
 - o Type of ultrasound system: SIEMENS S2000 18L6 HD probe or Philips IU22 with L12-5 linear probe and Epiq 7G with L12-3 linear probe.

- Type of gel used: ECG contact gel & high conductivity defibrillator: Hypoallergenic, Water-soluble, Non-irritating, Non-corrosive, Non-abrasive.
- Arterial ultrasound cervico-encephalic axes (axillary, carotid, vertebral arteries) and axillary and superficial femoral. Probe type: 4-9 MHz
- Recording of a number of images or video of sufficient quality and on a suitable medium for proofreading, archiving on site.
- Diagnostic :
 - Positive if sign of the hypoechoic halo present on the 2 ATS or on 2 different arterial axes (example a vertebral and an ATS, or right and left primitive carotid).
 - Negative if doubtful standard examination
 - One-sided halo
 - Iso/hyperechoic halo
 - Halo seen on other arteries but normal temporal arteries
- Disregard "isolated strictures" on the ATS.
- Take into account thrombosis on ATS (before a TAB).
- Describe atherosomatous plaques, carotid/axillary/subclavian/femoral stenoses).
- Blind review of the images (CDU n°1 and 2) by an expert: [name].

All patients with a "positive" echo-Doppler must be seen again by the same operator 3-4 weeks later, in order to determine the disappearance or persistence of the Halo; in case of persistence, it will be interesting to compare the echogenicity and to see the patient again at M3.

4.3.3- GCA processing protocol

No recommendations other than those of EULAR (The European League Against Rheumatism) and BSR/BHPR (25-27) for the starting dose and the corticosteroid tapering regimen (start between 0.5 and 1 mg/kg for 2 to 4 weeks, reduction for an objective of 15 to 20 mg of prednisone at 3 months, then more gradual reduction), idem vis-à-vis aspirin and the use of methotrexate.

Corticosteroid therapy can be started before Doppler ultrasound within a maximum period of < 7 days.

4.3.4- TAB protocol

Sampling :

- Performed < 14 days after start of corticosteroid therapy
- Size > 10mm
- Referred by ultrasound-Doppler or clinic if possible
- By a senior surgeon

Histological analysis:

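### Section 4.3.2 gives two opposite labels to halos on two non-temporal axes with normal temporal arteries (minor wording fix)

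*Combined protocol and SAP*

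**What the plan says.** The CDU rule is in section 4.3.2. An examination is positive when a hypoechoic halo is present on both superficial temporal arteries (ATS), or "on 2 different arterial axes (example a vertebral and an ATS, or right and left primitive carotid". Below that, next to one-sided halos and iso- or hyperechoic halos, the section lists "Halo seen on other arteries but normal temporal arteries" among the findings that are not positive.

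Other places bear on the same pattern:

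- Protocol Summary, Procedure: a definite halo sign "on two non-contiguous arterial segments will confirm the diagnosis of GCA, the patient will not undergo TAB". Biopsy is for the remainder: "In the event of a single halo, the patient will undergo a TAB", and likewise when there is no halo.
- Section 4.2.2.2, Visit 2: the same confirmation rule, again with no temporal artery required. A negative CDU leads to TAB.
- Section 4.2.2.2, Visit 3, for patients whose first CDU was positive: an axillary or common carotid halo prompts PET-CT or contrast CT in search of aortitis.
- Section 2.1: CDU performance is said to be "further increased if the analysis concerns in addition to the ATS, the subclavian, axillary and common carotid arteries". One reason given for a negative TAB is a "form exclusively involving the aorta and its large trunks".
- Section 3.1: the main objective covers the cervico-encephalic, axillary and superficial femoral arteries as well as the temporal arteries.

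The primary criterion (4.1.1) counts alternative diagnoses over 2 years among CDU-positive patients. Section 7.1 declares the algorithm valid only if there are none. Figure 1, the algorithm diagram, is not shown in the available text.

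**The concern.** The list item has no limit on the number of axes, and nothing says that the positive line takes precedence. An operator who reads the positive line sends a patient with bilateral carotid halos and normal temporal arteries to follow-up without biopsy. An operator who reads the list item sends the same patient to TAB.

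The pattern is foreseeable. Large arteries are scanned by design, and aortitis or arteritis of aortic branches on imaging is an entry route (5.1).

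The label also fixes membership of the primary PPV group and of the group examined at the interim look (7.4). It feeds the secondary criteria in 4.1.2 too: the TAB-positive rate in CDU-negative patients, the comparison of CDU-diagnosed with TAB-diagnosed patients, inter-operator discrepancies and avoided biopsies. A disagreement caused by the definition would be counted as operator disagreement.

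**Working it through.** **Step 1. Apply each rule to one patient:** hypoechoic halos on the right and left common carotids, both temporal arteries normal.

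| Text | Label |
|---|---|
| 4.3.2, positive line | Positive: this is the section's own example |
| 4.3.2, list item | Not positive: halos on other arteries, temporal arteries normal |
| Summary and 4.2.2.2, Visit 2 | Positive, if the two carotids count as non-contiguous segments |
| Summary, biopsy rule | No TAB: neither a single halo nor no halo |

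The two lines of 4.3.2 disagree.

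**Step 2. Look for the same fault elsewhere in the list.** Take a vertebral halo and a temporal halo on the same side. The positive line includes this pair by example. Read literally, the one-sided halo item excludes it. Rewording only the first item would leave this second overlap in place.

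**Step 3. Ask which label the rest of the text supports.** The Summary and 4.2.2.2 confirm the diagnosis without requiring a temporal artery. Sections 2.1 and 3.1 rely on the other arteries. The Visit 3 instruction expects axillary or carotid halos in positive patients, although those patients could also have temporal halos. The balance favours positive.

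**Step 4. Size.** The plan gives no figure for this pattern, so there is none to reproduce. Inputs:

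- 100 patients with GCA (Summary and 7.2).
- CDU sensitivity 96% (2.1), assumed to come from the cited series on temporal arteries and large vessels, because the reference number is garbled. This gives 100 × 0.96 = 96 positives.
- Assumed: n = 70 as a lower value, k = 1, 5 or 10 patients with the pattern, and an alternative-diagnosis rate p of 1% or 2% in all positives.

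Exact two-sided 95% lower limit of the PPV with no events: 0.025^(1/n).

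| Patients moved out (k) | Starting from n = 96 | Starting from n = 70 |
|---|---|---|
| 0 | 96.23% | 94.87% |
| 1 | 96.19% | 94.79% |
| 5 | 96.03% | 94.48% |
| 10 | 95.80% | 94.04% |

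The largest loss is 96.23 − 95.80 = 0.43 points, or 94.87 − 94.04 = 0.83 points.

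**Step 5. Effect on the zero-event rule.** Suppose one patient with the pattern has the only alternative diagnosis. Labelled positive, the PPV is 95/96 = 98.96% (exact 95% CI 94.33% to 99.97%), and the algorithm is not valid. Labelled negative, it is 95/95 = 100% (lower limit 96.19%), and the algorithm is valid.

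The chance that the verdict turns on the k patients alone is (1 − p)^(n − k) × [1 − (1 − p)^k]. For n = 96, p = 1%, k = 10, this is 0.99^86 × (1 − 0.99^10) = 0.4213 × 0.0956 = 4.0%. Over the assumed values the range is 0.3% to 4.0% for n = 96 and 0.5% to 5.4% for n = 70.

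The other positives fail the rule by themselves with probability 1 − (1 − p)^(n − k): 57.9% to 85.3% for n = 96, and 45.3% to 75.2% for n = 70.

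**The case against.** The case for leaving the text alone has four parts.

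- **Damaged layout.** The heading above the list does not read as a sentence, the indentation is lost, and 3.2 treats negative and doubtful as separate groups. A heading may therefore have dropped out. This makes the nesting uncertain. It does not remove the conflict, because the item is non-positive under either heading.
- **A residual list.** The list can be read as covering whatever fails the positive rule, with the specific carotid example governing the general item. This is probably what was meant, but the text does not say so.
- **Safeguards.** A preliminary meeting sets a consensus on halo interpretation, four operator meetings follow, and an expert reviews the images blind. These make divergent labels less likely. The expert still has to apply the same section.
- **Small effect on assumed inputs.** This stands. The frequency of the pattern is unknown, the positivity criterion behind the 96% cannot be seen, and n = 96 counts true positives only.

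A reader might infer something stronger: that the protocol sends patients with large-vessel disease to a biopsy likely to miss it, and so loses their diagnosis. The documents do not support that. The Summary and 4.2.2.2 point to no biopsy for this pattern. After a negative TAB, 4.2.2.2 explicitly allows the GCA diagnosis to be kept, with the same follow-up as CDU-positive patients.

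**Conclusion.** The contradiction is real in the available text of 4.3.2, and the severity is minor. A missing qualifier is the most likely explanation. The realistic consequences are an unnecessary biopsy for some patients and inconsistent classification between operators or centres.

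On the assumed inputs, the loss of PPV precision is under 1 point, and the validity verdict turns on these patients alone in 0.3% to 5.4% of cases. It would be tempting to say that the wording makes the primary conclusion unreliable. The figures do not show that: most of the fragility comes from the zero-event rule itself, which the other positives fail in 45% to 85% of the same scenarios.

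The textual finding needs none of these assumptions. It is limited to the text, because Figure 1 could not be checked.

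**What to change.** In 4.3.2:

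1. State that the negative or doubtful list applies only to findings that do not meet the positive rule. This also resolves the overlap between a one-sided halo and a same-side vertebral and temporal pair.
2. Reword the disputed item as *Halo on a single non-temporal axis with normal temporal arteries*.
3. Check Figure 1 and the source-language text for consistency.

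If TAB was in fact intended for this pattern, remove the carotid example from the positive line instead.

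Report the number of patients with halos on two or more non-temporal axes and normal temporal arteries. A sensitivity PPV with them moved to the other group is optional. Those managed as positive would have no TAB result, because biopsies not done cannot be recovered.

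The cost is a few words and one count. If the change is treated as substantial, 11.2 requires notification to the ethics committee and a favourable opinion before use.
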